A MOBILE PHONE SHORT MESSAGE SERVICE INTERVENTION TO INCREASE RETENTION IN HIV CARE AMONG HIV-POSITIVE MEN WHO HAVE SEX WITH MEN (MSM) IN PERU

WELTEL PERU

SUMMARY

Retention in care (or in care) for HIV is associated with increased survival and viral suppression, and with less transmission of the virus. HIV disproportionately affects men who have sex with men (MSM). In Peru, the HIV epidemic is concentrated in them (prevalence of 12.2%), while only 0.4% of the general population is HIV+. What is concerning is that MSM tend to have lower rates of retention in HIV care. Studies with text messages (SMS) have been reported to be effective in promoting testing for HIV and other sexually transmitted infections in MSM. Two-way text messaging (2-way, ie when the patient can reply) can provide a higher level of real-time support to patients. WelTel was the first randomized controlled trial to use this interactive approach and reported a significant increase in adherence and viral suppression. WelTel has been used successfully for HIV, asthma and tuberculosis. However, further studies are needed to evaluate the use of this strategy to increase retention in HIV care in resource-limited settings, such as in Latin America. The hypothesis is that an adapted version of WelTel can be used to implement a 2-way text message-based intervention, and to increase retention in care among HIV+ MSM in Peru.

To address the low retention in HIV care among MSM in Lima, we will use the WelTel system and its strategy managed by health providers consisting of sending reminder and informative SMS and differentiated follow-up. We will assess the efficacy of the intervention with a randomized controlled trial comparing the proportion of HIV+ MSM retained in HIV care among those who received the intervention versus the standard care arm, up to one year after enrollment. We will recruit 208 participants who will be randomly assigned (1:1) to an intervention group (receives the intervention with WelTel) and a control group (standard of care). Delivery of the intervention will take place over 6 months, and the main outcome to be measured will be retention in HIV care up to 1 year after enrollment.

ACRONYM

PLWHA: people living with HIV/AIDS. MSM: men who have sex with men.

ART: antiretroviral therapy.

SMS: short message service (short text message).

CD4: CD4 T lymphocyte cell.

CV: viral load. RR: relative risk.

MINSA: Ministry of Health.

PS: health provider.

STIs: sexually transmitted infections.

RESEARCHERS

[name] [name] [name] Dra. [name] Dra. [name]

INTRODUCTION

23.3 million people living with HIV/AIDS (PLWHA) are now receiving antiretroviral therapy (ART) and it is estimated that there will be 2.8 million more per year in the next 3 years (19). For continued access to ART and monitoring of clinical and virological progress, PLWHA must be maintained in high-quality care. **Retention in HIV care is associated with increased survival, viral suppression; and reduced HIV transmission and viral resistance** (20,21). Missing more than two HIV care visits increased mortality risk in a multicenter cohort study (HR = 3.61; 95% CI, 2.35-5.55) (21). Low retention in HIV care is a critical barrier to achieving optimal individual and community outcomes. Continuum of HIV care includes testing for exclusion, linkage to care, initiation of ART, retention, and adherence to therapy to achieve and maintain viral suppression. Since 2010, the number of new HIV infections in Latin America has remained stable, without significant decreases as observed in all other regions of the world (19). Viral suppression remains low in some regions: 22% in the Middle East and North Africa; 40% in the Caribbean; and 52% in Latin America (19). With the expansion of ART, urgent efforts are needed to retain PLWHA in care and thus reduce morbidity, mortality, and the incidence of new HIV-related infections (22-24).

HIV disproportionately affects men who have sex with men (MSM). MSM represent 41% of new infections in the region (19). In fact, MSM have a 27-fold higher risk of HIV infection than the general population (25). In Peru, the epidemic is concentrated among them (prevalence 12.2%), while only 0.4% of the general population is HIV+ (19,26). The incidence among MSM aged 18 to 29 years has increased substantially and 60% of new infections occur in this group (27,28). Of concern, HIV-positive MSM are less likely to remain in care than other population groups (29-33). In the United States, 54.3% retention in HIV care and 50.8% viral suppression were reported among MSM aged 20-24 years (32). In Peru, less than 50% of MSM have been tested for HIV and it is estimated that only 24% of those infected know their status (28). The Ministry of Health reported that retention in HIV care after the first year is 55%, which drops significantly during the second year (26). National viral suppression is only 36% (26).

Based on multiple studies that have shown efficacy, the World Health Organization (WHO) strongly recommends the use of text messages (mobile health) to improve adherence to ART (34-38). However, evidence on the impact of mobile health for retention in HIV care is scarce (39,40). Some studies in Africa concluded that short message service reminders (SMS or text messages) are effective in improving retention in HIV care in the general population (39). Until now, no controlled study has done the same with MSM, one of the populations most affected by HIV. Studies with MSM have reported good efficacy of SMS reminders to promote testing for HIV

and other sexually transmitted infections (STIs) (41-43). More trials with this key population are needed to evaluate the use of SMS to increase retention in HIV care in resource-limited settings, such as in Latin America (39).

Two-way communication (between patient and healthcare provider) with text messages (SMS) has the potential to provide comprehensive care through improved communication. A meta-analysis comparing one-way versus two-way SMS found that two-way SMS is the main driver for improving treatment adherence, while one-way messages have little or no benefit (44). Two-way messaging can provide a higher level of real-time support to patients. An evaluation of this strategy using the "behavior change wheel" suggested that the flow of support after an initial SMS is a key contributor to improving ART adherence (45). Health providers need appropriate tools to optimize the delivery of two-way text-based interventions and make them feasible and easy to deliver (38). An existing tool supported by evidence from previous studies can be adapted for use with MSM in Peru, with the aim of optimizing the delivery of a two-way text message intervention to increase retention in HIV care (38).

WelTel was the first randomized controlled trial using an interactive two-way text messaging approach that reported a significant increase in adherence and viral suppression in Kenya (RR for non-adherence: 0.81, 95% CI: 0.69 -0.94; RR for virologic failure 0.84, 95% CI: 0.71-0.99), as well as among HIV+ women in Vancouver, BC (38,46). WelTel is based on a well-structured platform that connects healthcare providers with patients through regular text messages. It uses a web-based program (software) (accessed through the Internet) with intuitive functionalities that allow providers to monitor, track and support large numbers of people (47). The platform allows addressing multiple morbidities, as well as different health services. The system has been tested in Kenya, Rwanda, South Africa, the United States, and Canada and has been used for other diseases such as tuberculosis and asthma (46,48,49). A recent study with WelTel in Kenya significantly improved Quality of Life scores ("the 4th 90") (40). HIV+ MSM in Peru may benefit from receiving an SMS-based intervention delivered through the WelTel platform to increase low retention in HIV care (retention = 50% at study site).

JUSTIFICATION

Peru is a relevant place to test an SMS intervention to increase retention in HIV care based on existing WelTel technology. The country has a high number of cell phone subscriptions (121 per 100 people), and smartphone use is also very common and constantly growing (50-52). Our preliminary data shows that Peruvian MSM are interested in receiving HIV prevention information via SMS (2,3,50,53). Other studies report that HIV+ MSM are interested in interacting with health providers to discuss HIV-related issues that may positively affect their retention in care (55). The proposed study will develop, implement, and evaluate an adapted version of WelTel to deliver a two-way interactive SMS intervention to increase retention among HIV+ MSM. WelTel has been used extensively in other resource-limited settings, and there is preliminary information in Peru to help tailor the content of such an intervention (3,4,12,40,43,49,55).

The use of a two-way SMS intervention to improve retention in HIV care among MSM is innovative. Globally, there are no published controlled studies on improving retention among HIV+ MSM that have used this approach and this study will be the first to evaluate this type of mHealth intervention in Peru. This study will provide evidence on the use of mobile health to improve retention in HIV care, where retention is currently very low. Retention has been the focus of fewer interventions compared to other steps of the HIV care continuum, and it is a crucial step because it involves multiple visits over time (35,57-59). This is the first study that will test the WelTel system in Latin America, specifically in Peru, where there are promising characteristics to carry out the intervention. We will adapt and validate the system for use in Spanish. We will test an already developed system that has the flexibility to add new features to improve patient follow-up.

OBJECTIVES

General Objective:

To assess the efficacy of a text message (SMS)-based strategy delivered with the support of a web tool (WelTel) to increase retention in HIV care in Peru.

Specific Objective:

To determine the efficacy of SMS-based intervention delivered through the WelTel system in increasing retention in HIV care compared to standard care.

Hypothesis:

An SMS-based intervention delivered through the WelTel system will increase retention in HIV care among MSM. We hope to increase retention in HIV care from 50% to 70%.

METHODS

Study Overview:

To address the low retention in HIV care among MSM in Lima, we will use the WelTel system and its strategy managed by health providers that consists of sending reminder and informative SMS and with differentiated follow-up. We will assess the efficacy of the intervention with a randomized controlled trial comparing the proportion of HIV+ MSM retained in HIV care versus the standard care arm up to one year after enrollment. Table 1 summarizes the exposures, results, and design.

Behavior Theory:

The behavior change wheel framework has been used to explain how WelTel can promote adherence to ART. The Capability, Opportunity, Motivation, and Behavior model is at the core of the theory (45). According to this model, the achievement of a behavior requires the presence of capacity, opportunity and motivation. To perform in a behavior, a person needs psychological (knowledge and skills) and physical capacity. Opportunity (physical and social) refers to factors that promote behavior. Physical opportunities are those that occur in the external environment, such as a physical reminder (SMS) to take medication. Social opportunities refer to non-physical factors, such as social norms and interpersonal influences. Motivation includes automatic and

reflexive processes that elicit behaviors such as emotions, habits, beliefs, and plans. Automatic processes are those that involve emotional responses, impulses, desires, and reflex responses, while reflective processes involve conscious planning and evaluation. This framework advocates identifying behavior change techniques as components of the intervention.

Only 1 behavior change technique has been identified for the automated text messaging component of the intervention: requesting/indicating the behavior. The behavior change techniques identified in WelTel were mainly related to its personalized communication component delivered to patients who reported a problem or query. These techniques were: a) eliciting/indicating the behavior, b) unspecified social support, c) reducing negative emotions, d) communication from a credible source, e) information about health consequences, f) social emotional support, g) practical social support, eh) instructions on how to perform a behavior. At WelTel, such behavior change techniques were linked to 5 intervention functions: environmental restructuring, empowerment, education, persuasion, and training.

Finally, to specify possible mechanisms of action to promote a behavior, such techniques and functions must be connected to influences on behavior following this model. The proposed mechanisms of action to facilitate adherence behavior in WelTel were: a) the delivery of an external trigger (SMS reminder to complete a behavior) and social support, to influence opportunities and automatic motivation through restructuring and environmental clearance; b) delivery of health-related information and social support to influence ability, opportunity, and motivation through education, persuasion, and training. We believe that retention in HIV care will be similarly influenced in our intervention.

General description:

This intervention will be designed for MSM who are HIV positive. We will recruit subjects 18 years of age or older. The intervention will begin one day after enrollment. The two-way SMS intervention will have four components: 1) an automated weekly SMS sent to ask how they are doing (basic follow-up); 2) phone calls from a health provider to participants who respond that they have a problem, or that they need support or some information that cannot be resolved by text message; 3) SMS reminder 1 week before an appointment for HIV care.

Design:

Randomized controlled trial.

Main result:

The primary outcome will be retention in HIV care for up to 1 year after enrollment. Participants will be classified as retained in care if they attend three HIV care appointments that are separated by 90 days or more within a one-year period (at the study HIV center) (64). Otherwise, they will be classified as not retained. The delivery of the intervention will last 6 months and the follow-up period to verify retention will last up to 12 months.

Main exposure:

Text message (SMS) based intervention delivered through the WelTel system by trained health providers.

Procedures:

- 1. **Recruitment and eligibility criteria**. We will identify and recruit 208 HIV+ MSM in the Cayetano Heredia Hospital HIV service for a period of up to 12 months. Eligible participants will be 1) men who have sex with men; 2) 18 years or older; 3) has been diagnosed HIV positive; 4) own a cell phone that can send and receive SMS; 5) resides in Lima; and 6) not be enrolled in another study that uses text messaging.
- 2. Enrollment and randomization: During enrollment, the recruiter will be blinded to assignment to the intervention group. The recruiter will obtain informed consent and instruct the participant on how he should interact if he starts receiving text messages (see appendix 1). Participants will be randomly assigned after providing their cell phone number and brief general information (first name, date of diagnosis, email). They will be assigned a study ID and randomly divided into intervention or control arm (1:1 ratio) using computer generated random numbers. Arm assignments will be in sequentially numbered sealed envelopes. Healthcare providers trained to administer the intervention will be informed by the research team when a new participant is enrolled in the intervention arm. Due to the nature of the study, healthcare providers and participants will not be blinded to group assignment. The participants assigned to the intervention arm will have their telephone numbers registered on the platform.
- 3. Intervention. We will use the WelTel platform. For 6 months, every Monday the system will send automatic SMS with the question "How are you?" or similar questions (How are you?; How are you doing?). Participants will be instructed to respond if they are okay ("All OK") or if they have a problem ("I want support"; "I'm not okay"). The provider will send a return SMS to participants who have a problem or query; or they will call those who need it. The WelTel program has a customizable dictionary that identifies the words (or phrases) that the administrator indicates; thus, the answers of the participants are automatically ordered to indicate who needs follow-up through a reply SMS or call. One week before each appointment for HIV care, health providers will send an SMS reminder (Table 1).
- 4. Standard care arm. In 2018, the government published new national guidelines for HIV care (65). After pre-test counseling, the diagnosis of HIV is made with two rapid tests. Those who test positive for both tests receive post-test counselling, including emotional support, and are linked to an ART initiation center, ideally within the same week. During the first medical appointment after diagnosis, laboratory tests including CD4 and viral load (VL) are requested. In most cases, initiation of antiretroviral treatment (ART) occurs at the second medical appointment when basic laboratory results are available. Currently, it is not mandatory to have CD4/CV results available to start ART. ART, viral load and CD4

lab tests are provided free of charge. It is recommended that patients have CD4 counts and viral load testing twice during the first year. A one-month supply of ART is initially provided. If patients are adherent, nurses dispense ART every 3 months and also assess adherence.

Table 1. Summary of the study: exposures, results and design.

Component	Sub-	Description						
	component							
	Basic follow-up	Weekly automatic SMS with the question "How are you?" or similar						
	SMS (check-in)	messages. This will be shipped for 6 months.						
Intervention	Calls	The provider can call participants who have a problem.						
arm	Appointment	SMS reminder one week before each appointment for HIV care.						
(exposure)	reminders							
	Primary	Retention in HIV care up to 1 year after enrollment, defined as attending 3						
Results		appointments that are 90 days apart within a 1-year period.						
	Desing	Randomized controlled trial with a parallel group.						
		We aim to increase retention in HIV care from 50% to 70%. With 104						
	Sample size	participants in each arm, we will have 80% power to detect this difference						
Design	Follow-up	6 months (intervention); 12 months (retention measure).						
	Theory	The behavior change wheel framework and its model of Capability,						
		Opportunity, Motivation and Behavior.						
	Standard of care	Post-test counselling, including emotional support and linkage to ART						
Control arm		initiation, ideally within a week. ART, CD4, and viral load laboratory tests are						
		provided free of charge in Peru.						

Analysis plan:

 Data sources for the main result. The main outcome to be measured will be retention in HIV care during the first year after enrollment. Retention in care will be considered if they attend 3 HIV care appointments that are at least 90 days apart within a one-year period (64). We will verify retention in HIV care with: study registration (enrollment) sheets, physical medical records from the HIV service, reception appointment notebooks, and with a final follow-up survey.

Health providers will enter the data from the enrollment registration sheets into a database that will be stored in a password-protected computer file. The data from the final follow-up online survey completed by the participants will be exported to the physical database and will be periodically deleted from the online survey system server. All data resulting from the interaction between providers and participants will be stored on the WelTel platform that has high security standards: encrypted, password protected and HIPAA compliant (*The Health Insurance Portability and Accountability Act*).

Statistic analysis. for the main outcome, we will compare the proportion of MSM who
were retained in care in both groups, as a cumulative incidence rate. If any variable of
interest is not balanced between intervention and control arms, we will calculate Mantel

Haenszel-adjusted relative risks (RR). For secondary outcomes, we will also assess differences in the proportion of participants.

3. **Calculation of the sample size**. We hope to increase retention in HIV care from 50% to 70% one year after enrollment in the study clinic among HIV+ MSM. With 104 participants in each arm, we will have 80% power to detect this difference.

Our main outcome is the degree of loss to follow-up. Retention in care at the study HIV service (as opposed to being lost to follow-up) is the primary outcome, and retention in any HIV clinic will be a secondary measure. Participants lost to follow-up will be considered as not retained. We will measure the retention in an establishment of the Ministry of Health (MINSA). MINSA provides care to more than 60% of Peruvians (73). Since retaining subjects in our public health system is an important goal, we have not adjusted the sample size calculation based on the potential loss of subjects to follow-up.

OPERATIONALIZATION OF VARIABLES

Table 2. Operationalization of variables.

Variable	Туре	Options	Source				
Age	Continuous	> 18	Online follow-up survey				
Education	Categorical	Secondary, Technical, Superior,	Online follow-up survey				
Civil status	Categorical	Single, Married, Outgoing, Coupled	Online follow-up survey				
Employment situation Categorical		Unemployed, Employed	Online follow-up survey				
Nationality	Categorical	Peruvian, Foreign	Online follow-up survey				
sexual orientation	Categorical	Gay, Bisexual, Straight	Online follow-up survey				
Diagnosis date	Date	Day month Year	Clinic history; dating record				
Treatment start date	Date	Day month Year	Clinic history; dating record				
Attended appointment dates	Date	Day month Year	Clinic history; dating record				
Viral load	Continuous		Clinic history				
CD4	Continuous		Clinic history				
alcohol use	numeric		Online follow-up survey				
Condom use, last encounter	Categorical	Yes, No	Online follow-up survey				
Email	Text		enrollment sheet				
Cell phone number	Numeric	NA	enrollment sheet				
Arm	Categorical	Control, Intervention	Study Database				
Retention in HIV care	Categorical	If not; Attend three appointments for HIV care that are 90 days or more apart within a one-year period (at the study HIV center)	Clinic history; dating record; online follow-up survey; WelTel system				

TIMELINE

Actividades		Year 1			Year 2			Year 3			Year 4					
	1	2	3	4	1	2	3	4	1	2	3	4	1	2	3	4
Recruitment/Enrollment																
Delivery of intervention																
Monitoring and analysis																
Manuscript development																

REFERENCES

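### Does the trial fail to answer its question because no outcome isolates attendance after the 6 months of messaging?

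*Combined protocol and SAP*

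**What the plan says.** Under Methods, Main result, a participant is retained if he attends visits that satisfy "attend three HIV care appointments that are separated by 90 days or more within a one-year period", at the study center; anyone else is not retained. The same paragraph sets the timing: "The delivery of the intervention will last 6 months and the follow-up period to verify retention will last up to 12 months". General description adds "The intervention will begin one day after enrollment", and Procedures, item 3 (Intervention), adds "One week before each appointment for HIV care, health providers will send an SMS reminder".

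The Analysis plan gives the window under Data sources for the main result: "The main outcome to be measured will be retention in HIV care during the first year after enrollment". Under Calculation of the sample size the target is worded as a rise "from 50% to 70% one year after enrollment in the study clinic". That section also says that "retention in any HIV clinic will be a secondary measure", with no time window, and that men lost to follow-up count as not retained. Table 2 lists the dates of attended appointments among the variables. The Standard care arm paragraph describes the usual rhythm: "If patients are adherent, nurses dispense ART every 3 months and also assess adherence".

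**The concern.** Three visits at least 90 days apart can fit into 180 days, and messaging runs to about day 183. If the enrollment-day visit counts, which the plan does not say, a man seen on days 0, 90 and 180 and never again could be classed as retained for the year. More generally, the outcome pools visits made during messaging with visits made afterwards. A positive result could therefore come from an effect that stops with the messages or from one that persists, although the dates needed to look are collected. The sample size section's wording of the target can also be read as status at month 12, which a cumulative three-visit rule does not measure. If the trial claimed a lasting effect, or presence in care at month 12, the planned outcomes could not support that claim.

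**Working it through.** **1. What the trial was sized for.** Inputs from Calculation of the sample size: 50% versus 70%, 104 per arm, 80% power. The plan states no alpha; two-sided 0.05 is assumed.

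- Uncorrected: n = [1.96 × √(2 × 0.6 × 0.4) + 0.8416 × √(0.25 + 0.21)]² / 0.20² = 93 per arm.
- Continuity-corrected: (93/4) × [1 + √(1 + 4/(93 × 0.20))]² = 102.8, so 103 per arm against the stated 104.

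The figure reproduces to within one man per arm. The trial is sized for one comparison, the proportion retained over the first year.

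**2. Outcome against question.** The Specific Objective is to increase retention compared with standard care. The Hypothesis names the same 50% to 70%. Study Overview, Main result, Table 1 and Data sources all place the measure within the year after enrollment. None of them asks whether attendance differs once messages stop. The sample size wording is the only one that could suggest a month-12 status, and the outcome definition in the same Analysis plan settles it.

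**3. Date arithmetic.** Earliest success = day of first counted visit + 2 × 90.

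| First counted visit | Earliest success |
|---|---|
| day 0 | day 180 |
| day 30 | day 210 |
| day 90 | day 270 |

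Only a first counted visit within about three days of enrollment allows success by day 183. Otherwise the rule itself requires a visit after messaging.

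**4. Can one primary result hide two late patterns?** Assumed model: visits due on days 90, 180, 270 and 360, attended independently. Case (a) puts the effect on the first two visits only; case (b) puts it equally on all four. The chance of any visit after day 180 is 1 − (1 − p)², where p is the attendance probability at each of the last two visits.

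- Enrollment visit counted (two of four needed): p = 0.386 gives 50%. Case (a), 0.621 then 0.386, gives 70%, with 62.3% attending late in both arms. Case (b), 0.508 throughout, gives 70%, with 75.8% versus 62.3% attending late, a difference of 13.6 points before rounding.
- Not counted (three of four needed): p = 0.614 gives 50%. Case (a), 0.838 then 0.614, gives 70%, with 85.1% late in both arms. Case (b), 0.728 throughout, gives 92.6% versus 85.1%, a difference of 7.5 points.

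So the primary result does not identify the late difference. In both cases, however, 70% versus 50% is a correct statement about the outcome the plan defines.

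**5. How often would a man be retained with no visit after messaging?** Under case (a) with the enrollment visit counted, exact 90-day spacing gives 0.621² × 0.614² = 14.5% of the intervention arm and 0.386² × 0.614² = 5.6% of controls. If the enrollment visit does not count, it is 0% in both arms.

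The 14.5% depends on near-exact spacing, since both gaps must reach 90 days and together not exceed about 183. Suppose the two visits fall uniformly within 7 days either side of days 90 and 180 (assumed), with deviations u and w. Success by day 183 needs 0 ≤ u ≤ w ≤ 3. In whole days that is 10 of 15 × 15 = 225 combinations, 4.4%; in continuous time it is 4.5/196 = 2.3%. With attendance probabilities held fixed, 14.5% falls to 14.5% × 0.044 = 0.6% or 14.5% × 0.023 = 0.3%.

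**6. What an added late outcome would deliver.** With 104 per arm and two-sided 0.05, exact power of the Pearson test is 57% for 62.3% versus 75.8%, and 41% for 85.1% versus 92.6%. The 95% CI half-width, 1.96 × √[(p₁(1 − p₁) + p₂(1 − p₂))/104], is 12.4 points against a 13.6-point difference and 8.5 points against a 7.5-point one. Such an outcome would often fail to separate the two patterns.

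**The case for a change.** The best case for acting is that persistence is a natural question. About half of follow-up lies after messaging, and the Introduction notes that retention falls over time. The mechanisms proposed under Behavior Theory include both an external trigger, which may stop working when messages stop, and education, which may not. The dates are already collected, and fixing a window in advance would prevent a data-driven choice in a trial whose providers and participants are unblinded. Correlated attendance does not remove the ambiguity: with a logit random intercept of SD 1 or 2, the persistent-effect late difference is 10.3 to 17.3 points, against 0 under case (a).

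What stands is that no planned outcome isolates months 6 to 12, so the primary result cannot support a claim of lasting effect. That limits what may be concluded; it does not show that the planned conclusion is wrong. The Introduction's remark concerns the second year, beyond this trial's follow-up.

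Two further points weaken the objection without settling it. Men lost to follow-up count as not retained, which might exclude a man who disappears after day 180, but loss is not defined. And appointment reminders have no end date of their own; only the general 6-month delivery statement places days 184 to 365 after messaging.

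Whether the enrollment visit counts is an unstated detail. Any one reading applies alike to both arms, so it affects the level of retention and the size of the difference, not the fairness of the comparison.

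**Conclusion.** The concern does not hold as a defect. The plan asks whether a 6-month messaging strategy raises retention over the first year, and a randomised comparison of the three-visit proportion answers that. The observation about months 6 to 12 is correct, but durability is a question the plan neither poses nor claims to answer. An extra secondary outcome would be a reviewer's preference, with 41% to 57% power in the cases meant to justify it. The loose time phrase in the sample size section is clerical, because the outcome definition in the same Analysis plan is clear.

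The late differences of 0, 7.5 and 13.6 points rest on the assumed quarterly calendar and independent attendance. The power figures also assume a two-sided alpha of 0.05. The judgement that nothing is wrong rests on the documents' stated objective and outcome, not on that model. It would change if the trial went on to claim a lasting effect from the primary result alone.
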